5. ANALYSIS SETS

5.1. SAFETY POPULATION

In Part A and Part B, the Safety Population will include all subjects who receive at least 1 dose of ALKS 4230. In Part C, the Safety Population will include all subjects who receive at least 1 dose of ALKS 4230 or pembrolizumab. The Safety Population will be used for all safety analyses.

5.2. ANTITUMOR EVALUABLE POPULATION

The Antitumor Evaluable Population consists of all subjects who complete two cycles of therapy and have at least one follow-up scan.

The Antitumor Evaluable Population will be used for the antitumor activity analyses.

5.3. PROTOCOL DEVIATIONS

All protocol deviations related to study inclusion or exclusion criteria, conduct of the trial, subject management, or subject assessment will be listed. The list of protocol deviations will be finalized per the protocol deviation and non-compliance (PDNC) management plan and will be reviewed by the Sponsor, the principal investigator, the study statistician, and the study medical monitor and finalized before database lock. Only major protocol deviations will be summarized.

5.4. PHARMACODYNAMIC POPULATION

The Pharmacodynamic Population consists of all subjects who received at least 1 dose of ALKS 4230 and have at least 1 available post-baseline pharmacodynamics measurement.

Subjects who may have had any AEs or protocol deviations that are deemed to impact the pharmacodynamics measurements may be excluded from the pharmacodynamics analysis and summary statistics, which will be documented in the clinical study report.

The Pharmacodynamic Population will be used for the pharmacodynamic parameter calculations, graphical displays of individual data, and the listings of cytokine concentrations and pharmacodynamic parameters.

Syneos Health # 1006212

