## 9.2. Infusion-Related Reactions

ALKS 4230 may be associated with infusion-related reactions, including pyrexia, tachycardia, and chills with onset 3-6 hours postinfusion. Infusion-related reactions should be treated at the discretion of the Investigator.

Refer to Section 8.4.3.1 for guidance around medications used for pretreatment.

Infusion-related reactions associated with the use of pembrolizumab should be managed in accordance with the prescribing information for pembrolizumab (Keytruda [pembrolizumab] USPI).

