#### 14.3.2. Pharmacokinetic and Pharmacodynamic Population

The PK population will consist of all subjects who received at least 1 dose of ALKS 4230 and have at least 1 measurable serum concentration of ALKS 4230 at any scheduled PK time point.

The PD population will consist of all subjects who received at least 1 dose of ALKS 4230 and have at least one available postbaseline pharmacodynamics measurement.

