2. PURPOSE

The purpose of this statistical analysis plan (SAP) is to ensure that the summary tables, data listings and figures (TLFs) which will be produced, and the statistical methodologies that will be used, are complete and appropriate to allow valid conclusions regarding the study objectives described in the latest study protocol.

2.1. **RESPONSIBILITIES**

Syneos Health will perform the statistical analyses and is responsible for the production and quality control of tables, figures and listings (TLFs) detailed in this SAP text/Mock tables for safety and anti-tumor endpoints.

Alkermes will be responsible for pharmacokinetic (PK), blood-related pharmacodynamics and immunogenicity analyses and reporting. Syneos will be responsible for tumor-related pharmacodynamics (PD) listing.

STDM and ADaM data files for tumor-related PD datasets that contain tissue biomarker end points will be produced by Syneos Health. Only STDM data files for PC, blood-related PD, and ADA datasets will be produced by Syneos Health. All the PK, ADA and bloodrelated PD analyses will be specified in a separate analysis plan.

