4.2. SECONDARY ENDPOINTS

- Serum concentrations of ALKS 4230 and descriptive PK parameters
- Presence of anti-ALKS 4230 antibodies in serum
- Immune (i-) ORR (iORR) based on Immune RECIST (iRECIST) guidelines (Seymour et al 2017)
- Disease control rate (DCR) based on RECIST guidelines and immune DCR (iDCR) based on iRECIST guidelines
- DOR based on RECIST guidelines and immune DOR (iDOR) based on iRECIST guidelines
- DRR for Part B and Part C Cohorts C5, C6, C7 only
- Progression-free Survival (PFS) and immune PFS (iPFS) for Part B and Part C Cohorts C5, C6, C7 only
- Numbers of circulating CD8 T cells, Tregs, and NK cells in peripheral blood
- Serum concentrations of IL-6 and other cytokines

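### SAP 5.4 adds a discretionary adverse-event exclusion to the pharmacodynamic summaries that the protocol does not have, with no criterion, decision-maker or timing

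*SAP*

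**What the plan says.** Protocol 14.3.2 admits to the PD population every subject with at least one dose of ALKS 4230 who also "have at least one available postbaseline pharmacodynamics measurement". It has no exclusion for adverse events or deviations.

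SAP 5.4 opens with the same definition and then adds: "Subjects who may have had any AEs or protocol deviations that are deemed to impact the pharmacodynamics measurements may be excluded from the pharmacodynamics analysis". The sentence extends to summary statistics and ends with a disclosure requirement, "which will be documented in the clinical study report". The next paragraph of SAP 5.4 assigns to the PD population the parameter calculations, "graphical displays of individual data, and the listings of cytokine concentrations and pharmacodynamic parameters".

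SAP 4.2 lists two PD secondary endpoints: "Numbers of circulating CD8 T cells, Tregs, and NK cells in peripheral blood" and "Serum concentrations of IL-6 and other cytokines". SAP 2.1 makes the sponsor responsible for blood-related PD and states: "All the PK, ADA and bloodrelated PD analyses will be specified in a separate analysis plan". SAP 6.7 nevertheless gives rules for values below quantification and missing values in cytokine and immunophenotype summaries. SAP 11, which records changes from the protocol's planned analysis, does not mention the exclusion.

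**The concern.** An analysis set should not depend on a post-treatment event that may be related to the outcome being summarised, least of all through an open-ended judgement made with the data in view. Here the exclusion can be triggered by any adverse event that somebody considers to have affected a PD value. If such events are more frequent among subjects with unusually high or low values, the remaining subjects no longer represent those treated.

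What is at stake is the reported description of the PD effect, a secondary objective in all three parts, and the PK-PD relationships described in Protocol 14.4.4. Protocol 14.2 plans no inferential testing and 14.4.4 makes PD descriptive, so no error rate is affected.

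**Working it through.** **1. The two definitions side by side.**

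| Feature | Protocol 14.3.2 | SAP 5.4 |
|---|---|---|
| Entry | At least one dose and one postbaseline PD value | Same |
| Exclusion for adverse events or deviations | None | Permitted at discretion |
| Criterion | Not needed | None stated |
| Decision-maker | Not needed | None stated |
| Timing | Not needed | None stated for adverse events |
| All-subjects summary alongside | Not needed | None stated |

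SAP 5.3 requires the protocol deviation list to be final before database lock. Nothing equivalent covers exclusions for adverse events.

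**2. Could the adverse events be related to the PD measures?** Protocol 9.2 says: "ALKS 4230 may be associated with infusion-related reactions, including pyrexia, tachycardia, and chills", and puts onset at 3 to 6 hours after infusion. The schedules of assessments (Protocol Tables 5 to 7) sample cytokines at 4 and 8 hours after the start of infusion, among other times. SAP 9.3 tabulates a decreased lymphocyte count as an adverse event, and the CD8 T, Treg and NK cells counted as an endpoint are lymphocytes. A relation is therefore plausible. The documents do not report one.

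**3. Does the clause reach IL-6 and the cell counts?** SAP 2.1 points to a separate plan, which is not among the documents. SAP 5.4 and 6.7 still carry cytokine and immunophenotype rules. Under SAP 2.1 and 4.6 the tumour-tissue PD data are only listed, so an exclusion from summary statistics has no evident object in this SAP other than blood PD. The text can be read either way.

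**4. Possible size (illustration only).** The documents give no PD variance, exclusion rate or correlation, so there is no plan figure to reproduce. Assume that log PD and a latent adverse-event severity are bivariate normal with correlation ρ, that the log-scale SD is s, and that the fraction f with the highest severity is excluded. Then

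retained / all geometric mean = exp[−ρ · s · φ(z) / (1 − f)], where z is the (1 − f) normal quantile.

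For f = 0.10: z = 1.282, φ(z) = 0.1755 and φ(z)/(1 − f) = 0.195. With s = 1.0:

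- ρ = 0: 1.00
- ρ = 0.3: exp(−0.0585) = 0.94
- ρ = 0.6: exp(−0.117) = 0.89
- ρ = 0.9: exp(−0.1755) = 0.84
- ρ = −0.6: exp(+0.117) = 1.12

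Over f = 5% to 20%, s = 0.5 to 1.5 and ρ = 0.3 to 0.9, the ratio runs from 0.98 to 0.62.

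**5. Small cohorts (illustration only).** Protocol 8.1 gives Part A cohorts of about 3 to 7 subjects, so one exclusion removes between 1/7 = 14% and 1/3 = 33% of a cohort. If the excluded value is assumed to be 5-fold higher than the others, the full/retained geometric-mean ratio is 5^(1/6) = 1.31 for one of six (retained mean 24% lower) and 5^(1/3) = 1.71 for one of three (42% lower). If it is 5-fold lower, the retained mean is 31% or 71% higher.

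**The case against.** The case for leaving the clause alone has real content.

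- **Scope.** IL-6 and circulating cells are blood PD, and SAP 2.1 sends blood PD elsewhere. This stands as a reason not to say that the clause biases those endpoints. It does not remove the defect, because SAP 5.4 and 6.7 leave the scope open.
- **Safeguards.** The clause is permissive, and exclusions must be documented in the study report. Individual graphs and listings follow the PD population, so excluded data may still be visible. Adverse events are analysed in the full safety population. All of this stands, but disclosure does not supply the all-subjects summary.
- **Legitimate purpose.** The wording concerns events that affect the measurement. Glucocorticoids, which Protocol 8.4.3 permits for immune-mediated events, might do so. That is a fair reason for a sensitivity summary. The wording is still loose enough to cover events that merely accompany the PD response.

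A reader might also infer three stronger points that the documents do not support.

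- **That the exclusion could distort the choice of dose**, since Protocol 8.1 bases the RP2D partly on PD. SAP 3.4 records the RP2D as already determined at 6 µg/kg.
- **That it removes the strongest responders.** No passage links these adverse events to higher PD values, and excluding subjects with low lymphocyte counts would push cell-count summaries upward.
- **That it flattens the dose-PD relationship.** No figure shows such exclusions increasing with dose.

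Calling the exclusion post hoc also goes too far. The possibility is pre-specified; the criteria and timing are not.

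**Conclusion.** The point holds as a defect in the analysis-set rule. SAP 5.4 departs from Protocol 14.3.2 through a discretionary exclusion based on post-treatment events, and SAP 11 does not record it. The exclusion can bias the descriptive PD summaries, but bias is not demonstrated. If the excluded events are unrelated to PD level there is none, and otherwise it may run either way. Every ratio and percentage above rests on assumed f, ρ, s or fold difference and shows only that the effect need not be negligible, particularly in small cohorts. Whether the clause governs IL-6 and circulating cell counts cannot be settled without the separate blood-PD plan. The change is worth making because it is cheap and gives a rule less open to bias.

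**What to change.** 1. Delete the reference to adverse events from the exclusion sentence in SAP 5.4, and make the protocol's PD population (at least one dose and one postbaseline PD value) the main set for all PD summaries.
2. Limit exclusions from the main analysis to technically invalid samples, for example mis-timed, mislabelled or failed in assay, identified before results are seen.
3. Show any exclusion for adverse events or their treatment, such as glucocorticoids, only as a sensitivity summary beside the full set, with criteria fixed before database lock.
4. State whether SAP 5.4 applies to the separate blood-PD plan, and use the same rule there.
5. List any remaining departure from Protocol 14.3.2 in SAP 11.

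The cost is wording in the SAP and a matching edit to the blood-PD plan, plus a second set of summaries if a sensitivity exclusion is wanted. The downside is slightly wider spread in the PD summaries.

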6. GENERAL ASPECTS FOR STATISTICAL ANALYSIS

6.1. GENERAL METHODS

- Data will be summarized for Part A, Part B, and Part C separately when analysis is applicable for the part. For Part A, the summary tables will be presented by dose cohorts (0.1 µg/kg, 0.3 µg/kg, 1 µg/kg, 3 µg/kg, 6 µg/kg, 8 µg/kg, and 10 µg/kg ALKS 4230) and overall, and data listings will be ordered by dose cohorts and subject ID. For Part B, the summary tables will be presented by expansion cohorts with specified tumor types (RCC and Melanoma) and overall, and data listings will be ordered by expansion cohorts and subject ID. For Part C, the summary tables will be presented by cohorts based on subject's tumor type and prior treatment with PD-1 or rollover from Part A or B (Safety Run-in 1 ug/kg, Cohort 1: PD-1/L1 unapproved tumor types plus Safety Run-in 3 ug/kg, Cohort 2: PD-1/L1 approved tumor types (PD-1/L1 reatment naïve), Cohort 4: Monotherapy Rollover, Cohort 5: Melanoma, Cohort 6: NSCLC, Cohort 7: SCCHN), and overall, and data listings will be ordered by cohorts and subject ID.
- The continuous variables will be summarized using number of observations (n), mean, standard deviation (SD), median, minimum, and maximum unless otherwise specified. All estimations will include a point estimate and the corresponding 95% confidence interval. All mean (arithmetic and geometric) and median values will be formatted to 1 more decimal place than the measured value. SD values will be formatted to 2 more decimal places than the measured value. Minimum and maximum values will be presented to the same number of decimal places as the measured value. The coefficient of variation (CV) % will be formatted to 1 decimal point.
- The categorical variables will be summarized using frequency counts and percentages of subjects. All percentages will be rounded to 1 decimal place. Number and percentage values will be presented as xx (xx.x%).
- P-values will be output in the format: "0.xxx", where xxx is the value rounded to 3 decimal places. Any p-value less than 0.001 will be presented as <0.001. If the p-value is returned as <0.999, then it will be presented as <0.999.
- Confidence intervals (CIs) will be presented as 2-sided 95% CIs, unless specified differently in specific analyses.
- For concomitant medications and AEs, which are not associated to a visit, the cycles are determined based on their start dates. For other collected data, the cycles are determined based on their visit dates. When there are multiple laboratory records for a scheduled visit, the one closest to the target date (relative to the Day 1 in that cycle) will be used for analysis. If there are 2 or more records (for repeated test, for example) with the same time period to the target date, the later one will be used for analysis unless specified differently in specific analyses.

- Partial AEs/concomitant medications start/end dates will be imputed on the rules specified in Section 6.3.1.
- The cumulative tumor response and AE data will be summarized for subjects who enter into the Extension Phase.
- All laboratory data will be reported using international system of units.
- All analyses will be performed using SAS® statistical software package, version 9.4 or higher.

6.2. KEY DEFINITIONS

6.2.1. Cycle 1 Day 1

Cycle 1 Day 1 (C1D1) is defined as the date of the first dose of ALKS 4230 in the first dosing cycle. For rollover patients, C1D1 is the date of first ALKS 4230 dosing for each part respectively.

6.2.2. Enrollment

A subject is considered enrolled onto the study if a patient signed a consent form. The enrollment date is set to consent date.

Screen failures will not be recorded in the database.

6.2.3. Treatment Period

The treatment period starts on C1D1 and lasts until the end of the treatment date collected in the database

6.2.4. Study Day

The study day is determined relative to C1D1 in the study, while the cycle day is the day relative to the first dose date in that cycle. The day of the first dose of study medication in Cycle 1 will be defined as Study Day 1. The day prior to the first dose of study medication is Study Day -1. There is no Study Day 0.

6.2.5. Cycle Start/End Day

The start date of each treatment cycle will be calculated based on study drug exposure records for each subject. The start date of the cycle will be the date when the subject receives the first study drug of the cycle, noted as S1, S2, S3, etc. For the Lead-In Monotherapy cycle, the start date will be the first date when the subject receives ALK 4230 Monotherapy. For the combination cycles, the start date will be the first date the subject receives the ALK 4230 + Pembrolizumab combination therapy.

Version V3.0

The end date of each cycle is calculated as the day before the start date of the following cycle: ie, $E_i = S_{i+1} - 1$. For the last cycle, the end date will be calculated based on the last study dose date. The cycle end date is the last dose date + 16 except when cycle 1 is the last cycle in Parts A and B, for which the cycle end date is the last dose date + 9.

6.2.6. Cut-Off Date of Final Analysis

This study has not specified the treatment duration. For the purpose of final analysis, the cut-off date of final analysis will be determined by the sponsor when more than 90% enrolled patients discontinued the treatment and all responders have been followed at least 6 months. This will be considered as the main analyses. A full set of SAP defined TLFs will be produced and used for preparing the clinical study report (CSR).

6.2.7. Baseline and Change from Baseline

Study Baseline

Baseline value is defined as the last value prior to the first dose of study treatment administration. This value could be the pre-infusion assessment on the first dose date or the assessment at the screening visit. If multiple values are present for the same date, the values from the last assessment will be used as the baseline unless specified. The standard 12-lead ECGs will be performed in triplicate 5 minutes apart at all time points outlined in the protocol. The median value of the last triplicate ECGs prior to the first dose of study treatment will be used for summary purposes.

Part C Baseline for Rollovers

Baseline value is defined as the last value prior to the first dose of study treatment administration in Part C. This value could be the pre-infusion assessment on the first dose date. If multiple values are present for the same date, the values from the last assessment will be used as the Part C baseline unless specified. The standard 12-lead ECGs will be performed in triplicate 5 minutes apart at all time points outlined in the protocol. The median value of the last triplicate ECGs prior to the first dose of study treatment will be used for summary purposes.

The rollover subjects have two baseline values. The study baseline values are used for Part A and Part B analysis, and Part C baseline values are used for Part C analysis.

Absolute change from baseline (CFB) = (post-baseline value - baseline value).

Fold change from baseline (FCB) = post-baseline value/ baseline value.

For the purpose of tabulations for lab, ECG and vital sign, the unscheduled post-baseline values generally will be excluded from summary tables, but will be included in the listing. Unscheduled visits will be considered for analyses of worst CTCAE laboratory grades.

Version V3.0

Syneos Health # 1006212

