#### 14.4.7. Safety Analyses

The safety population will be used for safety analysis.

Treatment-emergent AEs are defined as AEs that are newly occurring or worsening from the time of the first dose of study drug. Reported AE terms will be coded using Medical Dictionary for Regulatory Activities terminology, and the severity of the toxicities will be graded according to the NCI CTCAE (version 4.03 or higher) where applicable.

The number and percentage of subjects with treatment-emergent AEs will be summarized by dosing group and overall, by severity, by toxicity/severity grade, and by relationship to study drug. Serious AEs, Grade 3 or 4 AEs, and AEs contributing to discontinuation from the study will be summarized.

Observed values and change from baseline in vital signs, ECG, and laboratory parameters will be summarized by dosing group. Shift table and number (percentage) of subjects with potentially clinically significant values at any postbaseline visit will also be summarized as appropriate. In addition, hematological and chemistry laboratory parameters will be graded according to the NCI CTCAE (version 4.03 or higher) where applicable. The worst severity grade, time to maximum Grade 3 or 4 value, and time to resolution (return to baseline grade or below) will be summarized.

Concomitant medications will be coded using the World Health Organization Anatomical Therapeutic Chemical drug classification system. The number and percentage of subjects using concomitant medications will be summarized.

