6.4. VISIT WINDOWS

Data collected at unscheduled visits that occurred outside the time windows specified in the protocol (e.g., postdose laboratory tests done on days not specified in the protocol) will be included in the data listings but will not be included in analyses summarized by timepoint unless otherwise stated.

For summaries by time point, if data is collected at multiple time points within a protocol specified time window (protocol section 8.2), the result taken at the closest time to the planned nominal time point will be used, unless specified otherwise. If this time is equal to either side of the nominal time-point for 2 measures, the earlier measure will be taken.

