9.4. LABORATORY EVALUATIONS

Clinical laboratory data are collected at the time points specified in study procedures and flow chart. The assessments are presented in the table on next page.

Alkermes Protocol # ALK4230-A101

Version V3.0

Syneos Health # 1006212

Hematology	Biochemistry	Urinalysis
 Hematocrit Hemoglobin Red blood cell count Total and differential (absolute) white blood cell count Platelets 	General Chemistry Albumin Bicarbonate Calcium Chloride Creatine phosphokinase Glucose Magnesium 	 Bilirubin Color and appearance Glucose Ketones Leukocytes Nitrite Occult blood pH
 International normalized ratio Partial thromboplastin time / Activated partial thromboplastin time 	 Phosphorus Potassium Sodium Total protein Uric acid Liver Function Tests Alanine transferase Alkaline phosphatase Aspartate transferase Lactic dehydrogenase Total bilirubin Renal Function Tests Blood urea nitrogen Creatinine Thyroid Test Thyroid Test Thyroid-stimulating hormone Serum Tumor Marker CA125 (ovarian cancer subjects only) CA19-9 (gastric and pancreatic cancer subjects only) PSA (prostate cancer subjects only) CEA (colorectal cancer subjects only) 	 Protein Specific gravity Urobilinogen Microscopic examination of sediment, only if urinalysis dipstick results are abnormal. Microscopic examination is not needed if urinalysis is abnormal for bilirubin, glucose, or ketones. Microbiology (as Applicable) Blood Urine Other

Version V3.0

Syneos Health # 1006212

A serum or urine pregnancy test will be administered to all women of childbearing potential. At the screening visit, results must be negative for the subject to be eligible for the study.

Separate analysis table for CA125 for ovarian pts will be displayed.

In addition, the hematology, coagulation, and chemistry laboratory parameters will be graded according to NCI CTCAE (version 5.0 or higher) where applicable.

Subjects who meet the potentially clinically significant (PCS) criteria in selected lab parameters will be summarized by treatment cohort, the PCS is defined as Grade 3 or above per CTCAE.

Lab shift table of CTCAE grade (1 to 5) will be summarized from baseline grade to minimum, maximum, and final grade.

Number of subjects who meet the following liver function test criteria will be summarized and corresponding listing will be presented:

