• An elevated aspartate aminotransferase (AST) or alanine aminotransferase (ALT) laboratory value that is ≥3× the upper limit of normal (ULN) and an elevated total bilirubin laboratory value that is ≥2× ULN and an alkaline phosphatase laboratory value that is <2× ULN within 3 days.

The corresponding listing will present all AST, ALT, total bilirubin, and alkaline phosphatase laboratory data for any subject meeting the aforementioned criteria at least one time.

Listings will be provided for the hematology, coagulation, chemistry, urinalysis, and pregnancy tests results.

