9.6. ECG

The standard 12-lead ECGs will be performed in triplicate 5 minutes apart at all time points outlined in the protocol. The mean value will be used for summary purposes.

The QTcF Intervals fulfilling grade 3 or above per CTCAE will be tabulated separately.

Subjects who meet the potentially clinically significant (PCS) criteria in the QTcF will be summarized by treatment cohort, the PCS is defined as QTcF >=501 msec or >60 msec change from baseline.

The QTcF shift table of CTCAE grade (1 to 5) will be summarized from baseline grade to minimum, maximum, and final grade.

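### SAP 6.2.7 leaves unscheduled ECG and vital-sign results, and on its default reading unscheduled liver tests, out of the safety outlier counts, although the protocol plans counts at any postbaseline visit

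*SAP*

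**What the plan says.** **Default rule and exception.** For laboratory, ECG and vital-sign tabulations, SAP 6.2.7 states that "the unscheduled post-baseline values generally will be excluded from summary tables, but will be included in the listing". The next sentence gives the only named exception: "Unscheduled visits will be considered for analyses of worst CTCAE laboratory grades".

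**Tables that the rule touches.**
- SAP 9.6 counts subjects with QTcF outliers, where "the PCS is defined as QTcF >=501 msec or >60 msec change from baseline". It also tabulates QTcF of Grade 3 or above and a QTcF grade shift table.
- SAP 9.5 counts subjects with Grade 3 or higher vital signs and gives a grade shift table.
- SAP 9.4 counts subjects with AST or ALT at least 3×ULN, bilirubin at least 2×ULN and alkaline phosphatase below 2×ULN within 3 days. The matching listing shows these tests "for any subject meeting the aforementioned criteria at least one time".

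**Protocol.** Section 14.4.7 says that the "number (percentage) of subjects with potentially clinically significant values at any postbaseline visit will also be summarized as appropriate". SAP Section 11, which records departures from the protocol, covers durable response rate, irRC/iRECIST and an added PFS analysis. It does not mention unscheduled safety data.

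**Several records at one visit.** SAP 6.1 takes the laboratory record closest to the target date; if records are equally close, "the later one will be used for analysis unless specified differently in specific analyses". SAP 6.4, on summaries by time point, says that for two measures equally far from nominal time "the earlier measure will be taken".

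**The concern.** Unscheduled tests are usually ordered because something looks wrong. A rule that removes them from outlier counts can therefore lower those counts, and never raise them. For a by-visit mean, restriction to scheduled values is ordinary practice. For a table of subjects who ever crossed a threshold, it defeats the purpose.

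At stake is how a zero or a low count is read. Under the rule, an empty QTcF table would mean that no outlier occurred at a scheduled time, while Protocol 14.4.7 leads the reader to expect that none occurred at any postbaseline visit. Liver matters in particular because Protocol 5.3 names it as a toxicology target organ.

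**Working it through.** The plan gives no figure to reproduce. The check applies the rules to each table and then to the visit schedule.

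**1. Which tables does the exception reach?** It covers worst CTCAE *laboratory* grades.
- Worst single-analyte grades (AST, ALT, bilirubin): covered.
- Laboratory PCS counts, defined as Grade 3 or above: plausibly covered.
- QTcF outlier, grade and shift tables: not covered, since an ECG is not a laboratory test.
- Vital-sign PCS and shift tables: not covered, for the same reason.
- Liver composite: ULN multiples of several analytes, not a CTCAE grade, so not expressly covered.

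**2. What do scheduled times miss?**
- *ECG, Part B (Protocol 8.3.8):* screening, predose on Day 1 of each cycle, and EOT. An ECG taken during or after an infusion is unscheduled.
- *ECG, Parts A and C:* end-of-infusion and 4-hour ECGs are scheduled on Days 1 and 5 of Cycle 1; from Cycle 2 on-treatment ECGs are predose on Day 1.
- *Vital signs, Part B (Table 6):* on dosing days, up to 2 hours after infusion. Protocol 9.2 puts infusion-related reactions at 3–6 hours.
- *Chemistry, Parts B and C from Cycle 3 (Tables 6 and 7):* Days 1 and 5. The next Day 1 is Day 22, a gap of 22 − 5 = 17 days.
- *Extension Phase (Table 8):* chemistry and ECG every third cycle, 3 × 21 = 63 days. A footnote adds that laboratory samples are taken only if clinically indicated.

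**3. Chance that an episode meets no scheduled draw (Cycle 3 onward).** Put the draws at times 0 and 4 of a 21-day cycle and assume onset is uniform over the cycle. For an episode of length L days, with L at least 4, it is seen if onset lies in [−L, 4]:

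- P(seen) = (L + 4)/21
- L = 7: 11/21 = 52% seen, 10/21 = 48% missed
- L = 14: 18/21 = 86% seen, 3/21 = 14% missed

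Cycles 1 and 2 have more draws (Day 3 in both, Day 8 in Cycle 1, Day 15 in Cycle 2), so these figures do not apply there.

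**4. The 3-day liver window.** Days 1 and 5 are 4 days apart. From Cycle 3, scheduled values can normally meet the criteria only if every component qualifies at one draw. The window adds something only if follow-up draws count.

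**5. Rules applied to hypothetical records** (ALT, bilirubin, alkaline phosphatase as multiples of ULN):

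| Records | Result |
|---|---|
| Scheduled Day 5 (1.5, 1, 1); unscheduled Day 12 (4, 2.3, 1); next Day 1 (1.2, 1, 1) | Scheduled only: not counted. All records: counted |
| Day 8 (4.0, 2.3, 1.0) and same-day repeat (2.8, 1.8, 1.0) | Later record (6.1): not counted. Earlier record (6.4): counted |
| Day 8 (4.0, 2.3, 1.0), repeat on Day 10, target Day 8 | Day 8 is closest and kept: counted |

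**6. What one uncounted case does** (exact 95% CI, illustration only). With N = 41, 0/41 (0.0 to 8.6%) becomes 1/41 = 2.4% (0.1 to 12.9%). With N = 53, 0/53 (0.0 to 6.7%) becomes 1/53 = 1.9% (0.0 to 10.1%).

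**The case against.** The best reply is that this is a wording gap in descriptive tables. The rule says only that values are generally excluded. SAP 6.4 limits its own exclusion to summaries by time point. The liver screen uses any-time language ("for any subject meeting the aforementioned criteria at least one time") and a multi-day window. Excluded values are still listed, including in a chemistry listing not restricted to subjects who meet the liver criteria. Protocol 14.4.7 is itself qualified by *as appropriate*. No inferential testing is planned.

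Much of this stands for the liver table, where exclusion is the default reading and not a stated rule. It does not rescue QTcF or vital signs: the one named exception is confined to laboratory grades, and nothing in SAP 9.5 or 9.6 brings unscheduled values back. A listing also does not correct a count.

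A reader might infer more than the documents support:
- *That the primary safety endpoint is distorted.* TEAE tables are built from adverse-event records, and Protocol 13.1 requires clinically significant laboratory values to be recorded as adverse events. DLTs are summarized separately.
- *That worst laboratory values vanish.* The exception keeps unscheduled visits for worst laboratory grades.
- *That a repeat always replaces the abnormal value.* Under SAP 6.1 this happens only on a tie, and only for laboratory records. The second result that Protocol 8.1 requires to confirm a DLT-range value need not be on the same day.
- *That subjects with a Grade 0 baseline drop out of the shift tables.* SAP 9.4 says "Lab shift table of CTCAE grade (1 to 5) will be summarized from baseline grade to minimum, maximum, and final grade", but the range may simply name the CTCAE scale, and the table shells are in a separate document.
- *That 48% or 14% of cases are lost.* These are chances of meeting no scheduled draw under assumed uniform onset. Dosing is confined to Days 1–5, so onset may well not be uniform.

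**Conclusion.** The point holds at moderate importance. As written, SAP 6.2.7 builds the QTcF outlier, grade and shift tables and the vital-sign PCS and shift tables from scheduled values only. That departs from Protocol 14.4.7 without being declared in SAP Section 11. The composite liver table falls under the same restriction by default, but the wording leaves the choice to the programmer.

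The direction is known (counts can only be too low). The size is not: the documents give no event rates and no frequency of unscheduled testing. The schedule shows that the gap is real, most clearly for post-infusion ECGs in Part B and for chemistry after Day 5 from Cycle 3 in Parts B and C.

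The tie rules are a smaller, separate matter. SAP 6.1 is specific to laboratory records and SAP 6.4 is general, but they point in opposite directions, and 6.1 is not limited to by-visit summaries. On a tie under 6.1, a lower repeat can displace an abnormal value. Response analyses and the Simon designs are untouched.

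**What to change.** Replace the sentences on unscheduled values in SAP 6.2.7 with:

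> *By-visit summaries use scheduled values. The liver-criteria table and listing, and all laboratory, QTcF and vital-sign PCS, worst-grade and shift (minimum/maximum) tables, use every post-baseline result: scheduled, unscheduled and repeat.*

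State one tie rule, use it in both SAP 6.1 and 6.4, and limit it to by-visit summaries.

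The cost is SAP wording and a change of input records for the affected tables. No new data are needed. The downside is that outlier counts may rise slightly.
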